## SPECIFIC AIMS

Depression among adolescents has increased significantly over the past decade, and adolescent girls have a threefold incidence of depression as compared to their male peers. Nearly 4 in 10 girls will experience a major depressive episode during adolescence. Importantly, youth who experience difficulties with emotion regulation, which is the ability to manage emotions in order to engage in appropriate and goal-directed behaviors, are at greater risk for depression, and the parent-adolescent relationship strongly influences this risk. The parent-adolescent relationship is thus a prime target for intervention and prevention efforts for adolescent depression. The overall impact of the proposed study will be the development of a protocol to promote parenting practices in support of adolescent emotion regulation that may ultimately be used as an intervention in adolescent depression. This study combines: (1) hyperscanning, an innovative approach using concurrent functional magnetic resonance imaging (fMRI) to simultaneously measure neural responses of two interacting individuals; and (2) real-time fMRI (rt-fMRI) neurofeedback, a method used for training participants to regulate activity in a specific brain region. Our preliminary studies suggest that neurofeedback is effective in reducing symptoms of depression, and that supportive parent-child relationships are associated with increased activation in brain regions important for emotion regulation during parent-child interactions and with fewer depressive symptoms in adolescents.

Our long-term research goal is to implement an effective parenting-based intervention for adolescent depression. Building on pilot data from past projects separately utilizing fMRI hyperscanning and neurofeedback, the objective of the current study is to develop a dyadic fMRI neurofeedback protocol using hyperscanning that will train mothers to regulate their daughters' activation in a brain region associated with emotion regulation (i.e., anterior insular cortex [aIC]), as well as to promote synchronous parent-child brain activity, which we and others have shown to be associated with positive emotional outcomes. The study will test this protocol for feasibility with ten mothers and their psychiatrically healthy adolescent daughters (ages 13-17), with the eventual goal to test this in a sample of depressed adolescents in a future study. Participants will complete a resting-state fMRI scan at the beginning and end of each hyperscanning session. Participants will also complete an ecologically valid emotion discussion task during hyperscanning, in which the daughter will describe a recent situation when she experienced strong negative emotions. The mother will then respond to the daughter while the mother is simultaneously receiving dyadic neurofeedback (dnf) of the daughter's aIC activation with the goal of decreasing it. Following the conversation, both participants will be asked to mentally reflect on the discussion while both receiving dnf representing the synchrony between the mother's and daughter's aIC activation. We have the following specific aims:

**Aim 1. To develop and test the feasibility of a hyperscanning fMRI neurofeedback protocol in mothers and their adolescent daughters. Hypothesis 1A.** Mothers will perceive that they are able to influence their daughters' aIC activation using the daughter's fMRI neurofeedback signal (e.g., dnf), based on rating scales presented at the end of each run (i.e., average rating of ability to move bar  $\geq 5/10$ ). **Hypothesis 1B.** Mothers and daughters will be able to establish and maintain temporal synchronous aIC activation while reflecting on their interaction.

**Aim 2. To determine preliminary effects of neurofeedback on neural activation and emotional experience during the dyadic social interaction. Hypothesis 2A.** Mothers' own aIC activation while listening to their daughters will be positively correlated with that of their daughters' during the mothers' response. **Hypothesis 2B.** Stronger temporal synchrony and coupling between mothers' and daughters' aIC activation during the reflection condition will be associated with more validating statements made by the mother during the task and lower self-report ratings of negative emotions in both participants.

**Aim 3. To identify short-term effects of neurofeedback training. Hypothesis 3A (Exploratory).** Mothers' and daughters' neural activation of resting-state networks will be more temporally synchronous at the end of the hyperscanning session (following neurofeedback), as compared to their first resting-state fMRI scans in the hyperscanning session. **Hypothesis 3B.** Ratings of positive emotions will be higher and negative emotions will be lower following the hyperscanning session as compared to ratings taken before the scan.

[figure not shown]
The expected outcome of the proposed study is a rt-fMRI neurofeedback-hyperscanning protocol that will be available for implementation in future studies with larger samples in order to study its effects on adolescent depression. The protocol and data from the first five dyads will be used for a K award submission in the fall of 2019. A manuscript will be prepared and submitted following the end of data collection in the summer of 2020. The protocol developed in this study will provide the foundation for future prevention and intervention efforts aimed at the effects of parenting on the development of emotion regulation skills and depressive symptoms.

**SIGNIFICANCE:** Depression is a debilitating illness that often begins during adolescence. In 2015, an estimated 3 million adolescents aged 12 to 17 in the U.S. had at least one major depressive episode in the past year – an increase of 44% over the past ten years. The peak onset of depression is around age 15. For adolescent females, rates of depression are three times that of adolescent males, with some studies indicating that 50% of females will have an episode of depression during adolescence. Furthermore, higher rates of depression in females persist into adulthood, with serious consequences for social and emotional health and well-being. Therefore, it is critical to research and understand the precursors to the onset of adolescent depression and identify intervention targets that forestall depressive episodes and the resulting health effects. **Parenting and emotion regulation** are two key factors that affect risk for depression, with a significant impact on the development of mental health during childhood and adolescence. Emotion regulation difficulties are a core vulnerability that underlie adjustment problems that emerge during adolescence, including depression. How parents react to and socialize their children's emotion regulation is critical to youth's mental health. Numerous studies show better emotion regulation among children of emotionally supportive parents compared to emotionally unsupportive parents who ignore and sometimes denigrate their children's emotions. Children who have warm, open, and supportive relationships with their parents have more positive emotional and mental health outcomes. Fostering such relationships may therefore aid in the prevention of and intervention for adolescent depression. Parenting influences emotion processing and emotion regulation neurocircuitry, as well as the development of psychopathology. Supportive parenting is associated with adaptive structural changes in limbic-striatal brain regions over time and adaptive functional responses to emotional stimuli. Parents and adolescents with more synchronous resting-state networks have similar daily emotional synchrony, and adolescents who have greater synchrony with their parents also show higher levels of emotional competence. When listening to critical comments made by their mothers, adolescents exhibit increased brain activity (relative to neutral comments) in subcortical-limbic regions but decreased activity in regions subserving cognitive control of emotion, such as the dorsolateral prefrontal cortex (dIPFC) and caudal anterior cingulate cortex. These findings suggest that typically developing adolescents fail to recruit cognitive control networks to help them regulate emotion when listening to critical comments from their mothers. Using a similar task in a study conducted with adolescent girls, [name] (a mentor on the current proposal) and colleagues demonstrated that symptoms of anxiety and depression are associated with a blunted left amygdala response to maternal criticism and praise paired with increased right amygdala response to criticism. Taken together, these regions (dIPFC, anterior cingulate, amygdala) constitute an emotion regulation network in which the aIC plays a key role. Adolescents' regulation of the aIC through neurofeedback influences information flow between the amygdala and higher cortical structures such as the dIPFC. Additionally, across numerous studies depressed adolescents show hyperactivation of the right aIC. Parenting effects on aIC activation can be seen in child maltreatment, which is also associated with increased aIC activation. **Collectively, these findings support the scientific premise that parenting influences adolescents' emotion regulation-related neurocircuitry, and parenting alters functioning in brain regions that support emotional reactivity and regulation in response to feedback from parents.**

**INNOVATION:** This study will integrate two cutting-edge, state-of-the art neuroimaging methods: hyperscanning and neurofeedback. This is the first study to our knowledge to simultaneously scan two individuals while they are interacting and being provided with real-time dnf. Using these techniques, mothers will be able to see in real-time how what they say to their daughter affects her brain function, and they will be able to use this feedback to respond more effectively and supportively to her. This will also be the first study to our knowledge to utilize a neurofeedback signal indicative of inter-brain synchrony. Parent-child neural synchrony has been shown to be associated with emotional health, and this study provides the opportunity for mothers and daughters to receive neurofeedback on inter-brain synchrony in order to enhance it. Due to the high ecological validity of this paradigm, we expect effects to generalize to future real-world interactions between the participants after study completion.

**PRELIMINARY DATA:** The proposed emotion discussion task has been used in previous studies with parents and adolescents. Our lab has experience with both hyperscanning and neurofeedback with parent-adolescent dyads. In the past 18 months, 40 parent-adolescent dyads completed a free-speech conflict discussion task while undergoing hyperscanning. The currently proposed project builds on acquired experience and acquired data and analyses. Preliminary analyses provide support for targeting the aIC as a key region for emotion regulation within the context of the parent-adolescent relationship. Our recent project included a task wherein each participant was led to believe the other had made a costly error during a cooperative game. A

whole-brain analysis using the AFNI program 3dTcorrelate was conducted to identify brain regions where parent and adolescent activity was correlated during the 'costly error' condition, and evidence for co-activation was found in bilateral aIC (Figure 1). aIC activation can be successfully regulated with rt-fMRI neurofeedback in adults, adolescents, and children. Importantly, down-regulation of aIC activation is associated with reduced anxiety in phobic participants at 3-month follow-up and, in healthy adolescents, has effects on a network of regions associated with emotion regulation. The aIC is thus a prime target for dnf with the goal of increasing emotion regulation in adolescents.

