Parents will complete a phone screen to determine initial eligibility (see Inclusion/Exclusion criteria in **Table 2**). If initial study criteria are met, a 2-hour in-person lab visit will be scheduled where mothers and daughters will complete consent/assent; diagnostic interviews (the Mini-International Neuropsychiatric Interview [parent MINI 7.0, adolescent MINI KID 7.0]); surveys on emotion regulation, parenting practices, depression, and anxiety (Table 3); and additional screening. Survey data will be used for preliminary exploratory analyses. Based on data collected from the screening visit, participants will be invited to participate in the full study: a 4-hour visit where mothers and daughters will complete emotion ratings, mock scanner training, and fMRI tasks individually and together using hyperscanning (scan time = 16 min resting-state [2 runs], 7 min structural MRI, 40 min fMRI tasks, 10 min clinical MRI scans).

**Participants.** 10 adolescents (ages 13-17; all female) and their biological mothers, total  $N=20$ , recruited using electronic flyers distributed through local schools and from a previous lab project (Dyadic Inter-Brain Signaling study). Our sample will include ~40% from ethnic/racial minority groups.

**Consideration of biological variables.** This study will result in pilot data and a protocol for a future intervention study in depression. Scientific reasons to only include females are: (1) rates of depression are three times higher among females than males; (2) during adolescence, female and male brains develop at

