**Emotion Discussion with Dyadic Neurofeedback Task.** This task will be completed in the scanner using simultaneous hyperscanning data collection. Prior to the fMRI, adolescents (without the parent present) will be asked to think of recent situations when they were feeling strong negative emotions, such as anger, sadness, and/or anxiety. They will be informed that they will be talking to their mother about each situation during the scan. The mother (without the daughter present) will be provided with task instructions and informed that while talking to her daughter she will be receiving neurofeedback from a region in her daughter's brain. The mother will be told that her goal is to decrease activation in that region by calming her daughter and decreasing the intensity of her daughter's emotional response. The emotion discussion task will consist of four types of trials, each lasting 40s: Rest trials, Count trials, Discussion trials, and Reflection trials. During the first Discussion trial, the adolescent will describe the emotional situation. This will be followed by a second Discussion trial during which the mother will respond to the adolescent while receiving neurofeedback from the adolescent's aIC. This will be followed by a Count trial during which participants will mentally count backward from 300 by a number specified on the screen (for example, by 6: 300, 294, 288...) in order to bring aIC activation back to baseline. This will be followed by a 40s Rest period. Following the Rest trial, the adolescent will be provided 40s to respond to her mother (no neurofeedback presented), and the mother will subsequently respond again to the adolescent while receiving neurofeedback from her daughter's aIC. This will again be followed by a Count and Rest trial. Finally, both the adolescent and her mother will be asked to mentally (i.e., silently) reflect on the discussion while receiving neurofeedback representing the synchrony between both participants' aIC activation. This will be followed by another 40s Count trial and 40s Rest trial, for a total runtime of 8 minutes. Participants will complete three runs of the emotion discussion task with dnf, followed by a fourth transfer run in order to determine if the effects of the training persist. During the transfer run, the task will be exactly the same except no neurofeedback will be presented.

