**Hypothesis 1B.** *Mothers and daughters will be able to establish and maintain temporal synchronous aIC activation while reflecting on their interaction.* Correlations will be calculated between mothers' and daughters' aIC timecourses (Reflect vs Rest contrast).

**Hypothesis 2A.** *Mothers' own aIC activation while listening to their daughters will be positively correlated with that of their daughters' during the mothers' response.* The correlation between the mothers' and daughters' average beta weights for aIC activation during each participant's Listen trials will be calculated.

**Hypothesis 2B.** *Stronger temporal synchrony and coupling between mothers' and daughters' aIC activation during the reflection condition will be associated with more coded validation statements during the task and lower self-report ratings of negative emotions in both participants.* a) Coupling will be measured as the correlation between timecourses for aIC activation as described in Hypothesis 1B, transformed to z-scores (Fisher's r-to-z transformation). b) Participants will be asked to rate the intensity of various emotions they felt during the scan (0-10 Likert scale). Correlations will be calculated between the z-scores (a) and 1) the number of validating statements made by the mother across the scan and 2) ratings of negative emotions (b).

**Hypothesis 3A (Exploratory).** *Mothers' and daughters' neural activation of resting-state networks will be more temporally synchronous at the end of the hyperscanning session (following neurofeedback), as compared to their first resting-state fMRI scans in the hyperscanning session.* Similarity of resting-state networks will be evaluated as described in Lee et al. (2017). ICA will identify intrinsic resting-state networks at the group level. On the individual level, a matrix of correlation coefficients for all possible pairs of resting-state networks will be created and transformed to Fisher's z, then vectorized and correlated between each pair of mother-daughter dyads to determine the level of synchrony within the dyad. A paired t-test will be conducted to determine if there is a significant difference between resting-state synchrony at the beginning versus end of the scanning session.

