**Hypothesis 3B.** *Ratings of positive emotions will be higher following the hyperscanning session as compared to ratings taken before the scan.* Paired t-tests will be conducted separately for mothers and daughters to determine if ratings of positive emotions (e.g., "happy," "calm") made on a 0-10 Likert scale before the scan differ significantly from those made after the scan.

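### Aims 2 and 3 claim effects of neurofeedback, but start-versus-end tests in one group (Aim 3) and correlations across dyads (Aim 2) cannot attribute anything to it

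*Combined protocol and SAP*

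**What the plan says.** In Specific Aims, Aim 3 is "To identify short-term effects of neurofeedback training" and Aim 2 is "To determine preliminary effects of neurofeedback on neural activation and emotional experience during the dyadic social interaction". Both are worded as effects of the feedback.

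The design has one group: "10 adolescents (ages 13-17; all female) and their biological mothers". The task section gives every dyad the same order: "Participants will complete three runs of the emotion discussion task with dnf, followed by a fourth transfer run". Of that last run it says "During the transfer run, the task will be exactly the same except no neurofeedback will be presented". No sham, yoked, no-feedback or counterbalanced condition is described. The second resting-state scan and the post-scan ratings come after all of these runs.

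The tests are in ANALYSES:

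- **H3A** (labelled exploratory): a paired t-test on within-dyad similarity of resting-state networks, to determine "if there is a significant difference between resting-state synchrony at the beginning versus end of the scanning session".
- **H3B** (not labelled exploratory): paired t-tests, separately for mothers and daughters, of whether positive-emotion ratings given "before the scan differ significantly from those made after the scan".
- **H2A and H2B**: correlations across dyads, of mothers' with daughters' anterior insula responses, and of coupling with validating statements and negative-emotion ratings.

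The transfer run is introduced as a check on whether training effects last, but no analysis listed in ANALYSES uses it. No limit on attribution is stated anywhere.

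**The concern.** A start-versus-end difference in one group estimates the sum of everything that happened in between. Feedback is one component. The others are elapsed time, getting used to the scanner, changing head motion, counting and rest blocks, and the mother-daughter conversations. The paired t-test has no term that isolates feedback, so the quantity estimated is not the quantity named in Aim 3. H3B is the most exposed: ratings taken before and after a scanner session about upsetting events could change with no feedback at all.

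Aim 2 has a different gap. All dyads received feedback, so a correlation between dyads describes how two measures vary together under feedback. It does not show what feedback changed.

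At stake is how the results may be described. The plan foresees a manuscript and a career-award application, and the Innovation section expects effects to generalise to real-world interactions. A significant H3A or H3B, read under the present Aim 3, would be reported as an effect of neurofeedback.

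**Working it through.** The plan gives no alpha, power, effect size or derivation of its sample size, so there is no figure to reproduce. Two-sided alpha 0.05 and all shifts below are assumptions.

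**1. What lies between the two measurements.** From the task section, each run has four 40 s Discussion trials (daughter, mother, daughter, mother) and one 40 s Reflection trial. There are three feedback runs and one transfer run, each stated as 8 minutes.

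- Task time: 4 × 8 = 32 min.
- Discussion: 4 trials × 40 s × 4 runs = 640 s, about 10.7 min.
- Feedback on display: (2 mother responses + 1 Reflection) × 40 s × 3 runs = 360 s = 6 min. The daughter sees only the Reflection part: 40 s × 3 = 2 min.

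The visit description gives 40 minutes of fMRI tasks and the coding section mentions five conversations. Both would fit a fifth run (40 / 8 = 5). With five runs, discussion would be 5 × 160 = 800 s, about 13.3 min. No fifth run is described, so four is used here.

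**2. Planned paired t-test when feedback does nothing.** Let dz be the mean non-feedback change divided by the SD of the differences. With n = 10 and df = 9, the critical value is 2.262 and the noncentrality is dz × √10. The rejection probability is P(|T| > 2.262), with T noncentral t.

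| dz | noncentrality | probability of significance |
|---|---|---|
| 0 | 0 | 0.050 |
| 0.3 | 0.949 | 0.136 |
| 0.5 | 1.581 | 0.293 |
| 0.8 | 2.530 | 0.616 |

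The 95% confidence half-width is 2.262 / √10 = 0.72 SD of the differences.

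**3. H3A against mismatched pairs.** Ten mothers and ten daughters form 10 × 10 = 100 pairings: 10 true and 10 × 9 = 90 mismatched. Write the change in similarity for mother i with daughter j as common shift + mother effect + daughter effect + pair residual. Any complete re-pairing uses each mother and each daughter once. The common shift and the individual effects are therefore the same in every re-pairing, and only the pair-specific part can set the true pairing apart. The simulation used 3,000 replicates with 199 permutations each. Mother and daughter effects had SD 0.5 and residual variance was 0.5, so total variance was 0.25 + 0.25 + 0.5 = 1. There was no dyad-specific change.

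| common shift (SD) | planned paired t-test | permuted pairing |
|---|---|---|
| 0 | 5.0% | 4.8% |
| 0.3 | 13.2% | 4.8% |
| 0.5 | 29.2% | 5.3% |
| 0.8 | 61.8% | 4.7% |

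The Monte Carlo standard error near 5% is √(0.05 × 0.95 / 3000) = 0.4 percentage points.

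**4. The transfer run as a control.** Assume linear drift δ per run, independent run-level noise of variance 1, and no feedback effect. The mean of runs 1 to 3 minus run 4 has expectation δ(0 + 1 + 2)/3 − 3δ = −2δ and variance 1/3 + 1 = 1.33. In 40,000 simulated studies it rejects 17%, 31% and 69% of the time at δ = 0.2, 0.3 and 0.5. Run 3 against run 4 rejects 7%, 9% and 17%. Comparing run 4 with the linear extrapolation of runs 1 to 3 holds 5% if the drift really is linear, but its variance is 1 + 1/3 + 4 × 0.5 = 3.33, which is 3.33 / 1.33 = 2.5 times larger.

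**5. Aim 2.** No arithmetic is needed. H2A and H2B correlate measures across 10 dyads, and neither sets a feedback condition against a no-feedback condition. The planned task contrasts (Listen, Reflect, Count, Rest) do not do so either.

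**The case against.** The strongest reply is that this is a feasibility study and largely says so: "The study will test this protocol for feasibility with ten mothers and their psychiatrically healthy adolescent daughters". Aim 2 is called preliminary and H3A exploratory. The wording of H3A and H3B already compares the end of the session with its start, so only the aim headings are causal. That is fair, and it keeps the remedy small. It does not remove the mismatch: Aim 3 carries no hedge, H3B is not exploratory, and no limitation is stated.

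It is also right that the probabilities above are simply the power of a 10-pair t-test. They become false-attribution rates only if each significant result is credited to neurofeedback, which is what the Aim 3 heading invites.

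A reader might infer more than the documents support:

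- **That Aim 2 is also a start-versus-end test.** It is not; it rests on correlations.
- **That half an hour of talk separates the measurements.** The half hour is total run time; discussion takes about a third of it.
- **That every confounder pushes the predicted way, so the same result is to be expected without feedback.** Directions are not established. Describing anger, sadness or anxiety could lower positive ratings, and drowsiness or motion could act either way. At assumed shifts of 0.3 and 0.5, significance is less likely than not.
- **That the transfer run is a ready-made control.** It is always last, it precedes both post-session measures, and it was designed to test persistence. Successful training and no effect at all both predict little difference from the feedback runs.
- **That a significant H3A or H3B is the plan's ground for a depression trial.** No passage says this. The stated product is a protocol, and the award application uses the first five dyads only.

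**Conclusion.** The concern holds for the stated aims. Aim 3 names an attribution that a single-group, fixed-order, start-versus-end comparison cannot give. Aim 2 names one that between-dyad correlations cannot give. This follows from the design and needs no assumed number.

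The size is illustrative: 0.14, 0.29 or 0.62 probability of a significant change at session shifts of 0.3, 0.5 or 0.8, under an assumed two-sided 0.05 and n = 10. The plan's own data can remove shifts common to all pairs from H3A, at about the nominal 5% in the model simulated. They cannot separate feedback from the dyad's own conversation, and H3B has no internal control. The feasibility aim, Aim 1, is not affected by this point.

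**What to change.** 1. **Reword.** State Aim 3 as change from before to after the session, and Aim 2 as associations observed during the session. Add one sentence saying that neither can be attributed to neurofeedback without a comparison condition, which is a matter for a later study. For H3B this is the only available remedy. Report its changes as estimates with confidence intervals.

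2. **Add a reference for H3A.** Compute the start-to-end change in similarity for all 100 mother-daughter pairings. Compare the mean of the 10 true dyads with the mean of the 90 mismatched pairs, and test by permuting which daughter is paired with which mother. Keep the exploratory label. State that a positive result shows change specific to true dyads, net of shifts common to all pairs, and does not separate feedback from conversation.

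3. **Do not use feedback versus transfer runs as an attribution control.** If shown at all, report the contrast descriptively, with its fixed order and its purpose of testing persistence stated.

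The cost is a weaker stated claim, a few changed sentences and one small extra analysis. No added participants, arm or scan time are needed.
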